We designed this study to elucidate the role of metformin and combination of metformin and pioglitazone in reducing the levels of interleukin-6 and interleukin-8 in patients with PCOS. This will help us in deciding a better treatment regimen for patients with PCOS. Interleukin-6 and interleukin-8 may emerge as predictive biomarkers of treatment response.

2. Aims and objectives

OBJECTIVES:

The objectives of this study are

1. Primary

To investigate the changes in the levels of interleukin-6 and interleukin-8 after 3 months treatment with metformin alone and combination of metformin and pioglitazone in patients with PCOS.

2. Secondary

To evaluate insulin resistance in all the groups at baseline and after 3 months of treatment.

3. Hypothesis:

Combination of metformin and pioglitazone may decrease the levels of IL-6 and IL-8 in women with PCOS better than metformin.

4. Operational Definitions:

POLYCYSTIC OVARIAN SYNDROME: Polycystic ovarian syndrome, or PCOS, is a condition characterized by chronic oligo-anovulation, polycytic ovaries and hyperandrogenism.

METFORMIN: An oral hypoglycemic drug that decreases glucose production by the liver

and increases peripheral glucose uptake, used to treat type 2 diabetes.

PIOGLITAZONE: is a thiazolidinedione (TZD) with hypoglycemic (antihyperglycemic, antidiabetic) action to treat diabetes.

INTERLEUKIN-6 is a cytokine that acts as both a pro-inflammatory cytokine and an antiinflammatory myokine. It is in humans encoded by the IL6 gene (5).

INTERLEUKIN-8: is a chemokine produced by macrophages and other cell types such as epithelial cells, airway smooth muscle cells (6) and endothelial cells.

5. Materials and Methods:

a. STUDY DESIGN: Two-Arm Randomized Clinical trial.

b. STUDY SETTING: OPD patients in Mardan Medical Complex, Khyber Medical University

c. STUDY DURATION: Six Months after approval of proposal

d. SAMPLE SIZE:

The sample size was calculated using OpenEpi software. With an expected reduction in interleukin-6 and interleukin-8 values of 15% in the Metformin arm, we would need 102 women with PCOS to demonstrate a 40% reduction in interleukin-6 and interleukin-8 in the Metformin and Pioglitazone arm with a power of at least 80% and a ratio of 1 in the two arms.

Arm#1: 51 women with PCOS will be selected based on the inclusion and exclusion criteria. They will receive metformin according to the body weight with maximum dose of 1000 mg (BD) daily.

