7.2.5 Treatment discontinuation

The treatment of the patient or study on the subject will be discontinued in case of pregnancy or any disease given in exclusion criteria and in patient with hypersensitivity to drugs. There is no serious adverse effect observed after treatment discontinuation.

8. Assessment Plan: HISTORY RELATED QUESTIONS AND CLINICAL ASSESSMENT

Name:	Age:	Date:	
Addres	ss: Marital status:		Phone No:
•	Menstrual irregularity:		
•	Age of menarche:	_	
•	Hirsutism:		
•	Acne:		
•	Daily physical exercise:		
•	Infertility:		
•	Height (m)		
•	Weight (kg)		
•	BODY MASS INDEX (kg/m2):		_
•	Drug history (current and past me	dications)	:
•	Surgical history:	_	
•	BP:		

_

Pulse: _____

Schedule of assessments

	Screening	Baseline investigations	On treatment	End of treatment	
	14-21 days prior to registration	Within 7 days prior to registration	Within 3 days prior to first dose	After 3 months	
Informed consent					
Clinical assessment (mentioned above) Pelvic ultrasound					
right ovary and left ovary (10 or more follicles. 2 – 9 mm in diameter)					
Other imaging					
FBS RBS					
LH FSH Testosterone					
IL-6 IL-8					
HOME. IR					
Concomitant medications					
Adverse events					
Outcome events					

ASSESSMENT PHASE DEFINITONS AND SPECIAL CIRCUMTANCES

SCREENING

All screening will be done before registration of the patients.

BASELINE

All baseline investigations including (but not limited to) levels of interleukin-6 and interleukin-8, insulin resistance and pelvic ultrasound will be performed before giving treatment to the patient.

ON TREATMENT

Assessment during the treatment will be performed.

END OF TREATMENT

All baseline investigations including (but not limited to) levels of interleukin-6 and interleukin-8, insulin resistance and pelvic ultrasound will be performed 12 weeks after treatment.

FOLLOW UP AFTER TREATMENT

No follow up will be performed.

9. Outcomes and Endpoints:

The outcomes of the study is the change in the levels of interleukin-6 and interleukin-8 with the use of antidiabetic drugs (metformin alone and combination of metformin and pioglitazone). Other symptoms like hirsutism, polycystic ovaries and serum testosterone levels may decrease and menstrual cycles might become become regular.

10. Safety Reporting: PREGNANCY

Follow up in the treatment will be discontinued with pregnancy.

REPORTING OF SERIOUS ADVERSE EVENTS

Any adverse effects that occur during the treatment will be reported.

11. Treatment Information:

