EFFECTS OF METFORMIN AND COMBINATION OF METFORMIN AND PIOGLITAZONE ON PLASMA IL-6 AND IL-8 LEVELS IN POLYCYSTIC OVARIAN SYNDROME

Clinical trial registration number: NCT03117517

Date: 15/03/2018

Statistical analysis:

The normality of the data was tested using Kolmogorov-Smirinov and Shapiro-Wilk tests and histograms. FSH, LH, Prolactin, testosterone, IL-6 and IL-8 were not normally distributed and were log transformed for analysis. In the final results log transformed values were back transformed and presented as geometric means and confidence intervals. Patient demographic data were evaluated at baseline as descriptive statistics and presented as mean \pm SD. Wilcoxon signed rank test was used to analyze and compare number of follicles in right and left ovary in the two groups, and also between baseline and follow-up. Results were presented as Median (interquartile range). The baseline data of anthropometric, hormonal and inflammatory markers were compared between the two groups by independent sample t test. Comparison between baseline and after intervention (of 12 weeks) data was done by paired sample t-test for both groups independently. Post intervention comparison between the two groups was also done by independent sample t-test. The change taking place between baseline and after 12 weeks due to intervention was calculated as difference or Δ . Δ was calculated as value at 12 weeks – value at baseline for hormonal, inflammatory and ovarian size variables. The Δ between the two groups was compared by independent sample t-test. P < 0.05 was considered statistically significant. All analyses were performed using SPSS software, version 21 "SPSS (IBM, Armonk, NY, USA).

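### IL-6 and IL-8 each get two unranked between-arm t-tests, neither adjusted for baseline, and the scale of Δ is not stated

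*SAP*

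**What the plan says.** The SAP (Statistical analysis) plans two between-arm comparisons of each marker after treatment. One uses the 12-week level: "Post intervention comparison between the two groups was also done by independent sample t-test". The other uses the change: "The Δ between the two groups was compared by independent sample t-test". Baseline values are compared between arms in a separate t-test but enter neither comparison as a covariate. The only decision rule is "P < 0.05 was considered statistically significant".

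On scale, the SAP says "FSH, LH, Prolactin, testosterone, IL-6 and IL-8 were not normally distributed and were log transformed for analysis", with results back-transformed to geometric means. It then defines the change without naming a scale: "Δ was calculated as value at 12 weeks – value at baseline for hormonal, inflammatory and ovarian size variables". Ovarian size falls under that same rule and is not listed as transformed.

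The protocol speaks of change. Its primary objective is "To investigate the changes in the levels of interleukin-6 and interleukin-8 after 3 months treatment" and section 9 says "The outcomes of the study is the change in the levels of interleukin-6 and interleukin-8". The hypothesis in section 3 is comparative: the combination "may decrease the levels of IL-6 and IL-8 in women with PCOS better than metformin". Section 12 plans an independent-sample t-test between arms on a mean difference in the marker values, without saying whether that means change or level.

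**The concern.** The hypothesis is a between-arm question, and the plan gives two answers to it for each marker without saying which one counts. One t-test can be significant while the other is not, and reporting whichever succeeds raises the false-positive rate.

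Neither test makes full use of the baseline measurement. The 12-week comparison ignores it. Δ subtracts it, which fixes the baseline slope at 1 whatever the data show. ANCOVA estimates that slope, and so is at least as precise as either apart from the trivial cost of estimating it.

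The scale of Δ matters too. As an illustration, a 30% fall from a baseline of 10 gives a raw Δ of −3.0 and from a baseline of 14 a raw Δ of −4.2, while the log Δ is log(0.7) = −0.357 in both. For skewed markers, a raw Δ lets high-baseline women dominate the comparison.

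**Working it through.** **Inputs from the documents.** 51 per arm, falls of 15% and 40%, power 80% (Protocol 5d); significance level 0.05 (SAP; taken as two-sided, since neither document says).

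**Assumed, because the documents do not give them.** Log-scale SD 0.6 to 0.8, equal at both times; correlation r between baseline and 12 weeks of 0.3 to 0.7.

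**1. The plan's own figure.** 102 is reproduced if 15% and 40% are treated as two proportions with pooled variance: (1.960 + 0.842)² × 2 × 0.275 × 0.725 / 0.25² = 50.08, so 51 per arm and 102 in total. This calculation corresponds to neither SAP t-test and supplies no SD.

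**2. Relative variances on the log scale.** 12-week value: 1. Δ: 2(1 − r). ANCOVA: 1 − r².

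| r | 12-week | Δ | ANCOVA | ANCOVA ÷ better t-test |
|---|---|---|---|---|
| 0.3 | 1 | 1.40 | 0.91 | 0.91 |
| 0.5 | 1 | 1.00 | 0.75 | 0.75 |
| 0.7 | 1 | 0.60 | 0.51 | 0.85 |

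The better t-test is the 12-week value below r = 0.5 and Δ above it. ANCOVA is ahead of both throughout.

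**3. Power.** The log-scale effect is |log(0.60) − log(0.85)| = 0.348. A closed-form check for the 12-week value at SD 0.6: SE = 0.6 × √(2/51) = 0.119; 0.348/0.119 = 2.93; power ≈ Φ(2.93 − 1.96) = 83%. Simulation (20,000 trials per row, bivariate lognormal values) gives, in percent:

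| Log SD | r | Log Δ | 12-week log | Log ANCOVA | One t-test significant, the other not | Raw Δ | ANCOVA at 0.025 |
|---|---|---|---|---|---|---|---|
| 0.6 | 0.3 | 68.4 | 82.9 | 85.7 | 25.2 | 43.2 | 78.1 |
| 0.6 | 0.5 | 82.8 | 82.6 | 91.4 | 20.1 | 55.2 | 86.0 |
| 0.6 | 0.7 | 96.1 | 82.7 | 98.0 | 17.6 | 71.9 | 96.2 |
| 0.8 | 0.3 | 45.4 | 58.3 | 62.0 | 32.5 | 24.0 | 50.4 |
| 0.8 | 0.5 | 59.1 | 58.4 | 70.7 | 32.3 | 30.5 | 60.1 |
| 0.8 | 0.7 | 80.5 | 58.6 | 85.9 | 36.2 | 42.2 | 78.4 |

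- ANCOVA over the better log-scale t-test: from 98.0 − 96.1 = 1.9 to 70.7 − 59.1 = 11.6 points.
- ANCOVA over the worse: from 91.4 − 82.6 = 8.8 to 85.9 − 58.6 = 27.3 points.
- Raw Δ below log Δ: from 45.4 − 24.0 = 21.4 to 80.5 − 42.2 = 38.3 points.
- Under no effect, each test alone rejects in 4.6% to 5.5% of trials, so none is invalid.

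**4. False positives when the tests are unranked.** Within a marker, the 12-week and Δ statistics correlate √((1 − r)/2) = 0.592, 0.500 and 0.387 at r = 0.3, 0.5 and 0.7. From correlated z statistics, with between-marker correlation 0 to 0.5, the chance of at least one significant result is:

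| Tests | Either direction | False claim that the combination is better |
|---|---|---|
| One marker, one test | 5% | 2.5% |
| One marker, two tests | 8.8% to 9.4% | 4.4% to 4.7% |
| Two markers, one test each | 9.0% to 9.8% | 4.4% to 5.0% |
| Two markers, two tests each | 15.6% to 17.8% | 7.8% to 9.1% |

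**The case against.** **The protocol already points to Δ.** Objective and outcome both speak of change, so Δ can be read as the test of the endpoint and the 12-week comparison as additional. That is the likelier reading, but neither document states it, and the SAP, which carries the later analysis detail, lists both tests on equal terms.

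**Log minus log is the natural reading of Δ.** I agree, which is why the raw-Δ figures are conditional. The doubt remains because a single rule covers transformed and untransformed variables.

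**ANCOVA is an efficiency preference.** True: the t-tests are valid. If Δ is primary and correlation is high, the gain is small: at r = 0.7, 98.0 − 96.1 = 1.9 points (SD 0.6) or 85.9 − 80.5 = 5.4 (SD 0.8). But the correlation is not given, and ANCOVA removes the need to guess it.

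**The four-test error rate presumes a rule the documents do not contain.** This stands in part. Objective, hypothesis and outcome all name both markers. If both must succeed, having two markers adds no inflation. The two tests per marker still do: a false claim of superiority on one marker, when the other truly responds, can reach about 4.7% instead of 2.5%. When neither responds it is about 0.2% to 1.0%. The documents do not say that both are required.

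**Disagreement is not contradiction.** Correct: the 18% to 36% are trials with one test significant and the other not, not tests pointing in opposite directions.

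**Conclusion.** The point holds. For its main comparison the SAP leaves open which of two t-tests decides and on which scale Δ is taken, and it does not adjust for a baseline that was measured. This should be corrected, but it does not invalidate the trial.

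That log ANCOVA beats both t-tests is firm across the assumed range; how much it gains depends on the assumed SD and correlation. The inflation to about 9% per marker is nearly independent of those assumptions, but applies only if either test may be relied on. The 16% to 18% figure needs the further assumption that either marker may count. The loss of 21 to 38 points for raw Δ applies only if Δ was in fact computed on untransformed values.

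**What to change.** In the SAP:

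- Name one primary between-arm analysis per marker: ANCOVA of log(12-week value) on arm and log(baseline value), reported as an adjusted ratio of geometric means with 95% CI.
- Define Δ for IL-6 and IL-8 as log(12-week) minus log(baseline), and label the Δ and 12-week t-tests supportive.
- State whether success needs either marker (then apply Holm) or both (no adjustment between markers).

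Bring Protocol section 12 into line. Its non-parametric fallback and its logistic regression on ROC cut-offs are separate matters that this change does not settle.

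The cost is some wording and one regression per marker in SPSS, with no new data. If Holm applies, its worst case is a marker tested at 0.025. That costs ANCOVA from 98.0 − 96.2 = 1.8 to 62.0 − 50.4 = 11.6 power points in these scenarios.

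The SAP is written in the past tense. If results had already been seen, the ANCOVA must be labelled a post hoc re-analysis and reported beside the t-tests as written.
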